5.2.4 Selected Adverse Events

To further elucidate potential clinical implications of ARIA findings, patients will be contacted up to 1 week before each MRI is performed and asked if they have experienced CNS adverse events. The eliciting of these adverse events should be

according to Section 5.3.2. The adverse events collected in this prospective fashion will be distinct from other adverse events and summarized separately in the clinical study report. Additional data on associated symptoms (as defined on the eCRF) and safety MRI scans will be collected for the following selected adverse events:

- ARIA-E: ARIAs suggestive of vasogenic edema and sulcal effusions
- ARIA-H: ARIAs suggestive of microhemorrhages and hemosiderin deposits

5.3 METHODS AND TIMING FOR CAPTURING AND ASSESSING SAFETY PARAMETERS

The investigator is responsible for ensuring that all adverse events (see Section 5.2.1 for definition) are recorded on the Adverse Event eCRF and reported to the Sponsor in accordance with instructions provided in this section and in Sections 5.4–5.6.

For each adverse event recorded on the Adverse Event eCRF, the investigator will make an assessment of seriousness (see Section 5.2.2 for seriousness criteria), severity (see Section 5.3.3), and causality (see Section 5.3.4).

5.3.1 Adverse Event Reporting Period

Investigators or their designees will seek information on adverse events at each patient contact. All adverse events, whether reported by the patient or noted by study personnel, will be recorded in the patient's medical record and on the Adverse Event eCRF.

After informed consent has been obtained **but prior to initiation of study drug**, only serious adverse events caused by a protocol-mandated intervention (e.g., invasive procedures such as biopsies, discontinuation of medications) should be reported (see Section 5.4.2 for instructions for reporting serious adverse events).

After initiation of study drug, all adverse events, regardless of relationship to study drug, will be reported until 52 weeks after the last dose of *study drug during Part 1 and until 4 or 16 weeks, as applicable, after the last dose of study drug during Part 2*. After this period, the investigator should report any serious adverse events that are believed to be related to study drug treatment (see Section 5.6).

5.3.2 Eliciting Adverse Event Information

A consistent methodology of non-directive questioning should be adopted for eliciting adverse event information at all patient evaluation timepoints. Examples of non-directive questions include the following:

“How have you felt since your last clinic visit?”

“Have you had any new or changed health problems since you were last here?”

5.3.3 Assessment of Severity of Adverse Events

Table 4 provides guidance for assessing adverse event severity.

Table 4 Adverse Event Severity Grading Scale

Severity	Description
Mild	Discomfort noticed, but no disruption of normal daily activity
Moderate	Discomfort sufficient to reduce or affect normal daily activity
Severe	Incapacitating with inability to work or to perform normal daily activity

Note: Regardless of severity, some events may also meet seriousness criteria. Refer to definition of a serious adverse event (see Section 5.2.2).

5.3.4 Assessment of Causality of Adverse Events

Investigators or their designees should use their knowledge of the patient, the circumstances surrounding the event, and an evaluation of any potential alternative causes to determine whether or not an adverse event is considered related to the study drug, indicating "yes" or "no" accordingly. The following guidance should be taken into consideration:

- Temporal relationship of event onset to the initiation of study drug
- Course of the event, considering especially the effects of dose reduction, discontinuation of study drug, or reintroduction of study drug (where applicable)
- Known association of the event with the study drug or with similar treatments
- Known association of the event with the disease under study
- Presence of risk factors in the patient or use of concomitant medications known to increase the occurrence of the event
- Presence of non-treatment-related factors that are known to be associated with the occurrence of the event

For patients receiving approved AD treatments, causality will be assessed individually for each protocol-mandated therapy.

5.3.5 Procedures for Recording Adverse Events

Investigators or their designees should use correct medical terminology/concepts when recording adverse events on the Adverse Event eCRF. Avoid colloquialisms and abbreviations.

Only one adverse event term should be recorded in the event field on the Adverse Event eCRF.

5.3.5.1 Injection Reaction

Individual signs and symptoms of injection-site reactions (e.g., erythema, pain) should be reported on the Injection-Site Reaction eCRF. The overall diagnosis of injection-site reaction should be captured on the Adverse Event eCRF. Systemic reactions should be recorded as a single diagnosis.

5.3.5.2 Diagnosis versus Signs and Symptoms

For adverse events other than injection-related reactions, a diagnosis (if known) should be recorded on the Adverse Event eCRF rather than individual signs and symptoms (e.g., record only liver failure or hepatitis rather than jaundice, asterixis, and elevated transaminases). However, if a constellation of signs and/or symptoms cannot be medically characterized as a single diagnosis or syndrome at the time of reporting, each individual event should be recorded on the Adverse Event eCRF. If a diagnosis is subsequently established, all previously reported adverse events based on signs and symptoms should be nullified and replaced by one adverse event report based on the single diagnosis, with a starting date that corresponds to the starting date of the first symptom of the eventual diagnosis.

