5.3.5.3 Adverse Events Occurring Secondary to Other Events

In general, adverse events occurring secondary to other events (e.g., cascade events or clinical sequelae) should be identified by their primary cause, with the exception of severe or serious secondary events. However, medically significant adverse events occurring secondary to an initiating event that are separated in time should be recorded as independent events on the Adverse Event eCRF. For example:

- If vomiting results in mild dehydration with no additional treatment in a healthy adult, only vomiting should be reported on the eCRF.
- If vomiting results in severe dehydration, both events should be reported separately on the eCRF.
- If a severe gastrointestinal hemorrhage leads to renal failure, both events should be reported separately on the eCRF.
- If dizziness leads to a fall and subsequent fracture, all three events should be reported separately on the eCRF.
- If neutropenia is accompanied by an infection, both events should be reported separately on the eCRF.

All adverse events should be recorded separately on the Adverse Event eCRF if it is unclear as to whether the events are associated.

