5.7.2.2 CNS Symptoms Temporally Associated with ARIA-E MRI Findings

In this report, symptomatic ARIA-E is defined as onset or worsening of CNS symptom(s) that is/are temporally associated with ARIA-E MRI findings. A programmatic approach to capture symptomatic ARIA-E will be adopted in the analysis, since CNS symptoms have not been consistently captured in the CRF AE form. For programmatic retrieval, CNS symptoms temporally associated with ARIA-E MRI findings were defined as all AEs from the Nervous System Disorders and Psychiatric Disorders SOCs that had onset between 4 weeks prior to ARIA-E onset through ARIA-E resolution, and not falling under ARIA-associated PTs.

The list of ARIA-associated PTs include:

- Amyloid related imaging abnormalities
- Amyloid related imaging abnormality-microhaemorrhages and haemosiderin deposits
- Amyloid related imaging abnormality-oedema/effusion
- Cerebral amyloid angiopathy
- Brain oedema
- Vasogenic cerebral oedema
- Brain stem microhaemorrhage
- Cerebellar microhaemorrhage
- Cerebral microhaemorrhage
- Cerebral haemosiderin deposition
- Magnetic resonance imaging head abnormal
- Superficial siderosis of central nervous system

The CNS symptoms temporally associated with ARIA-E MRI findings (programmatic retrieval) will be listed and summarized by previous randomization and APOE ϵ 4 genotype, and overall. A listing of AE reported as Symptoms of ARIA-E (eCRF) will be provided as well.

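### The OLE summary of symptomatic ARIA-E can miss patients whose symptoms were recorded under the ARIA-E diagnosis, because site-reported symptoms are only listed

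*Protocol*

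**What the plan says.** **Recording rules.** For events other than injection-related reactions, Protocol 5.3.5.2 tells sites that "a diagnosis (if known) should be recorded on the Adverse Event eCRF rather than individual signs and symptoms". If the diagnosis comes later, "all previously reported adverse events based on signs and symptoms should be nullified and replaced by one adverse event report based on the single diagnosis". Section 5.3.5.3 says that secondary events "should be identified by their primary cause, with the exception of severe or serious secondary events". The same section keeps some events separate: medically significant secondary events "that are separated in time should be recorded as independent events on the Adverse Event eCRF", and so are events whose link to each other is in doubt. ARIA-E is exempted in neither section.

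**ARIA-specific collection.** Under Protocol 5.2.4, patients are asked about CNS events in the week before each MRI. Events collected this way are to be kept distinct and summarised on their own in the study report. The section adds: "Additional data on associated symptoms (as defined on the eCRF) and safety MRI scans will be collected for the following selected adverse events". ARIA-E is one of those selected events.

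**Analysis.** OLE SAP 5.7.2.2 defines symptomatic ARIA-E by CNS symptoms that coincide in time with the MRI finding. It identifies them by program as "all AEs from the Nervous System Disorders and Psychiatric Disorders SOCs that had onset between 4 weeks prior to ARIA-E onset through ARIA-E resolution", excluding a list of ARIA-associated preferred terms. Its stated reason is inconsistent capture of CNS symptoms on the adverse event form. For site-reported symptoms it says only: "A listing of AE reported as Symptoms of ARIA-E (eCRF) will be provided as well". OLE SAP 5.7.3 then summarises ARIA-E with CNS symptoms, and no rule adds the site-reported symptoms to that count.

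**The concern.** The recording rules and the retrieval rule pull in opposite directions. A mild headache that the site attributes to ARIA-E, and records as Protocol 5.3.5.2 and 5.3.5.3 direct, may survive only as an ARIA-E record plus an entry in the associated-symptom data. The program needs a separate CNS record and discards ARIA terms, so it cannot see that patient. Nullification can also remove the pre-diagnosis symptom records that the four-week look-back is designed to find.

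Safety and tolerability at higher doses is the primary objective of the OLE, and ARIA-E is an identified risk. Symptom status also mattered in the conduct of the trial: Protocol 5.1.4.2 handles symptomatic ARIA-E of any size under a different rule from asymptomatic ARIA-E with a low Barkhof score. A patient managed as symptomatic could therefore be tabulated as having ARIA-E without CNS symptoms.

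**Working it through.** The plan gives no figure for this point, so there is nothing to reproduce. The check is to follow a symptom through the two sets of rules.

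| Symptom in a patient with ARIA-E | Record under the protocol | Found by the OLE SAP program? |
|---|---|---|
| Attributed to ARIA-E, neither severe nor serious, no other rule applies | ARIA-E diagnosis only; symptom in associated-symptom data | No: ARIA terms are excluded |
| Recorded first, ARIA-E diagnosed later | Symptom record nullified (5.3.5.2) | No, unless 5.2.4 is read as keeping it |
| Elicited in the week before an MRI | Kept distinct (5.2.4) | Yes, if kept as an adverse event record in the two organ classes and the window |
| Severe or serious | Separate record (5.3.5.3) | Yes, same condition |
| Link to ARIA-E unclear, or medically significant and separated in time | Separate record (5.3.5.3) | Yes, same condition |
| Unrelated CNS or psychiatric event in the window | Separate record | Yes, although not a symptom of ARIA-E |

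The first two rows are the possible misses and the last is the possible overcount. The documents do not say whether 5.2.4 or the nullification rule in 5.3.5.2 prevails when both apply.

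**Illustration of scale.** Inputs:

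- 230 OLE patients (OLE SAP section 1).
- Predicted two-year ARIA-E occurrence p of 5% to 41% across the titration groups (Protocol Table 1). Applying each extreme to all 230 patients gives outer bounds.
- About 90% of ARIA events asymptomatic in Study WN25203 (Protocol 1.3.3), hence about 10% symptomatic, assumed here to carry over to ARIA-E in the OLE.
- f, the share of symptomatic cases whose symptoms exist only inside the ARIA-E record. The documents give no value, so it is varied.

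Symptomatic cases = 230 × p × 0.10. True cases left in the summary = 230 × p × 0.10 × (1 − f).

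- p = 0.05: 230 × 0.05 = 11.5 ARIA-E patients, 1.15 of them symptomatic.
- p = 0.41: 230 × 0.41 = 94.3 ARIA-E patients, 9.43 of them symptomatic.

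| f | Left, p = 0.05 | Left, p = 0.41 | As % of ARIA-E patients |
|---|---|---|---|
| 0 | 1.15 | 9.43 | 10.0 |
| 0.25 | 0.86 | 7.07 | 7.5 |
| 0.50 | 0.58 | 4.7 | 5.0 |
| 0.75 | 0.29 | 2.36 | 2.5 |
| 1 | 0 | 0 | 0 |

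**Net direction.** Let g be the number of patients counted only because of an unrelated event. The net error is g − f × (symptomatic cases). Assume g = 1 and f = 0.5. With 1.15 symptomatic cases the net error is 1 − 0.575 = +0.4; with 9.43 it is 1 − 4.715 = −3.7. The sign changes within the plausible range, so the documents do not fix it.

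**The case against.** The strongest reply is that the protocol has an ARIA-specific rule. Section 5.2.4 keeps CNS events elicited before each MRI distinct, which points to separate records that the program could find. Section 5.3.5.3 also keeps severe, serious and doubtful-link events separate, together with medically significant events separated in time, and doubtful attribution is realistic for CNS symptoms in this population. This stands, and it rules out any claim that the records are certain to be lost. It does not close the gap: symptoms arising at other times are not covered by 5.2.4, and nothing says that 5.2.4 overrides nullification.

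A second reply concerns the SAP's stated reason. A reader might infer that the SAP contradicts itself by retrieving from the form it calls inconsistent. The sentence can equally mean that symptoms were not consistently linked to ARIA-E, and a time-based rule that needs no attribution is a fair answer to that. The temporal rule is worth keeping, but it cannot recover symptoms that were never kept as adverse events.

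Third, the listing may consist of adverse event records flagged as ARIA-E symptoms. If so, many would already be in the programmatic count, and adding them would change little. If the symptoms sit only in the associated-symptom fields, even the listing may not show them. The eCRF is not available to settle this, and a concordance count would.

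Finally, the OLE analyses are descriptive, and cases are likely to be few enough to check by hand. That limits the seriousness of the point. It does not help a reader who has only the summary table.

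**Conclusion.** The mismatch is real but conditional. Symptomatic cases recorded under the ARIA-E diagnosis can be missed by the summary in OLE SAP 5.7.3, and unrelated CNS events in the window can be counted. How often either happened depends on site practice.

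A reader might go further and infer that true symptomatic cases are systematically removed at data entry, that the symptomatic share is therefore understated, or that the summary consists mainly of unrelated events. The documents support none of these. The rules that keep records separate are substantial, the folded share is unknown, and missed and spurious cases work in opposite directions.

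The range of about 1 to 9 symptomatic cases is only an illustration. It rests on model-predicted ARIA-E occurrence and on a symptomatic share for all ARIA events in another study at 105 and 225 mg, not for ARIA-E at doses up to 1200 mg. If numbers are of that order, one or two misclassified patients could visibly change a table split by previous randomization and genotype. The point merits a cheap correction to the analysis plan and does not call the safety analysis as a whole into question.

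**What to change.** In OLE SAP 5.7.2.2 and 5.7.3, define ARIA-E with CNS symptoms per patient in three ways:

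- (a) site-reported on the eCRF, including the associated-symptom data collected under Protocol 5.2.4;
- (b) the existing programmatic retrieval;
- (c) either (a) or (b).

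Summarise all three by previous randomization, by APOE ε4 genotype and overall, and add a concordance count of (a) against (b). There is a precedent in the same plan: OLE SAP 5.7.2.1 both lists and summarises the signs and symptoms of administration-related reactions. It would also help to state which recording rule sites were expected to follow for ARIA-E symptoms, so that disagreement between (a) and (b) can be interpreted.

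The cost is SAP wording and a few table columns, using data that the protocol already has sites collect. The reported symptomatic share may rise, because (c) cannot be smaller than (b). Since (c) keeps any unrelated events picked up by (b), it should be shown beside (a) and (b) and not in place of them.

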5.3.5.3 Adverse Events Occurring Secondary to Other Events

In general, adverse events occurring secondary to other events (e.g., cascade events or clinical sequelae) should be identified by their primary cause, with the exception of severe or serious secondary events. However, medically significant adverse events occurring secondary to an initiating event that are separated in time should be recorded as independent events on the Adverse Event eCRF. For example:

- If vomiting results in mild dehydration with no additional treatment in a healthy adult, only vomiting should be reported on the eCRF.
- If vomiting results in severe dehydration, both events should be reported separately on the eCRF.
- If a severe gastrointestinal hemorrhage leads to renal failure, both events should be reported separately on the eCRF.
- If dizziness leads to a fall and subsequent fracture, all three events should be reported separately on the eCRF.
- If neutropenia is accompanied by an infection, both events should be reported separately on the eCRF.

All adverse events should be recorded separately on the Adverse Event eCRF if it is unclear as to whether the events are associated.

5.3.5.4 Persistent or Recurrent Adverse Events

A persistent adverse event is one that extends continuously, without resolution, between patient evaluation timepoints. Such events should only be recorded once on the Adverse Event eCRF, unless the severity increases. If a persistent adverse event becomes more severe, it should be recorded as a separate event on the Adverse Event

eCRF. The initial (less severe) adverse event report should be updated to indicate that the event resolved on the date just prior to the day the event became more severe. If a persistent adverse event becomes serious, it should be recorded as a separate event on the Adverse Event eCRF and reported to the Sponsor immediately (i.e., no more than 24 hours after learning that the event became serious; see Section 5.4.2 for reporting instructions). The initial (non-serious) adverse event report should be updated to indicate that the event resolved on the date just prior to the day the event became serious.

A recurrent adverse event is one that resolves between patient evaluation timepoints and subsequently recurs. Each recurrence of an adverse event should be recorded separately on the Adverse Event eCRF.

5.3.5.5 Abnormal Laboratory Values

Not every laboratory abnormality qualifies as an adverse event. A laboratory test result must be reported as an adverse event if it meets any of the following criteria:

- Is accompanied by clinical symptoms
- Results in a change in study treatment (e.g., dose modification, treatment interruption, or treatment discontinuation)
- Results in a medical intervention (e.g., potassium supplementation for hypokalemia) or a change in concomitant therapy
- Clinically significant in the investigator's judgment

It is the investigator's responsibility to review all laboratory findings. Medical and scientific judgment should be exercised in deciding whether an isolated laboratory abnormality should be classified as an adverse event.

If a clinically significant laboratory abnormality is a sign of a disease or syndrome (e.g., alkaline phosphatase and bilirubin 5× the ULN associated with cholecystitis), only the diagnosis (i.e., cholecystitis) should be recorded on the Adverse Event eCRF.

If a clinically significant laboratory abnormality is not a sign of a disease or syndrome, the abnormality itself should be recorded on the Adverse Event eCRF, along with a descriptor indicating if the test result is above or below the normal range (e.g., "elevated potassium," as opposed to "abnormal potassium"). If the laboratory abnormality can be characterized by a precise clinical term per standard definitions, the clinical term should be recorded as the adverse event. For example, an elevated serum potassium level of 7.0 mEq/L should be recorded as "hyperkalemia."

Observations of the same clinically significant laboratory abnormality from visit to visit should not be repeatedly recorded on the Adverse Event eCRF, unless the etiology changes. The initial severity of the event should be recorded, and the severity or seriousness should be updated any time the event worsens.

If a patient develops moderate to severe neutropenia (absolute neutrophil count $< 1000/\text{mm}^3$) in the absence of an identified cause, investigators should consider temporary discontinuation of the study drug. Neutrophil counts should be monitored according to the local guidelines. Reintroduction of study drug should be done only after the investigator discusses the case with the Sponsor's Medical Monitor.

5.3.5.6 Abnormal Vital Sign Values

Not every vital sign abnormality qualifies as an adverse event. A vital sign result must be reported as an adverse event if it meets any of the following criteria:

- Is accompanied by clinical symptoms
- Results in a change in study treatment (e.g., dose modification, treatment interruption, or treatment discontinuation)
- Results in a medical intervention or a change in concomitant therapy
- Is clinically significant in the investigator's judgment

It is the investigator's responsibility to review all vital sign findings. Medical and scientific judgment should be exercised in deciding whether an isolated vital sign abnormality should be classified as an adverse event.

If a clinically significant vital sign abnormality is a sign of a disease or syndrome (e.g., high blood pressure), only the diagnosis (i.e., hypertension) should be recorded on the Adverse Event eCRF.

Observations of the same clinically significant vital sign abnormality from visit to visit should not be repeatedly recorded on the Adverse Event eCRF, unless the etiology changes. The initial severity of the event should be recorded, and the severity or seriousness should be updated any time the event worsens.

5.3.5.7 Abnormal Liver Function Tests

The finding of an elevated ALT or AST ($> 3 \times$ the upper limit of normal [ULN]) in combination with either an elevated total bilirubin ($> 2 \times$ the ULN) or clinical jaundice in the absence of cholestasis or other causes of hyperbilirubinemia is considered to be an indicator of severe liver injury. Therefore, investigators must report as an adverse event the occurrence of either of the following:

- Treatment-emergent ALT or AST $> 3 \times$ ULN in combination with total bilirubin $> 2 \times$ ULN
- Treatment-emergent ALT or AST $> 3 \times$ ULN in combination with clinical jaundice

The most appropriate diagnosis or (if a diagnosis cannot be established) the abnormal laboratory values should be recorded on the Adverse Event eCRF (see Section 5.3.5.2) and reported to the Sponsor immediately (i.e., no more than 24 hours after learning of the event), either as a serious adverse event or an adverse event of special interest (see Section 5.4.2).

